AIM 2: To assess daily patterns of e-cigarette use (including dual use of combustible cigarettes), product satisfaction, and nicotine cravings with use of 4.5% vs 0 mg (placebo) e-cigarette; and

AIM 3: To compare the effect of nicotine e-cigarettes (4.5%) vs placebo e-cigarettes on smoking reduction at 1, 3 and 12 weeks post baseline assessment.

Study design

This pilot study will be a two-arm, randomized controlled trial. We will randomize 50 participants into each intervention arm. Participants will be recruited through advertisements placed in Craigslist and other social media as well as flyers placement in NYU venues and street distribution with contact details for how to get in touch with a Research Assistant. The randomization sequence will be prepared by the study statistician. Participants will be randomized to one of the two arms: e-cigarettes with nicotine cartridges or e-cigarettes with placebo cartridges (0mg). Participants and research assistants will be blind to the allocation of nicotine or placebo e-cigarettes as there are no difference in appearance or odor of the mist emitted from the e-cigarettes with and without nicotine containing cartridges.

Figure 1. Study design

Study participants

Inclusion criteria: ages 21-35 (must present proof of age), daily smoker, smokes at least 10 cigarettes a day (verified by a CO level of 8 ppm or above), interested in reducing CPDs, able to provide consent, uses a cell phone and is willing/ able to receive and respond to daily text messages regarding his/her cigarette use and e-cigarette use on his/her cell phone, and willing to use an e-cigarette for 3 weeks.

Exclusion criteria: Pregnant and/or breastfeeding (self-reported), current use of smoking cessation medications (including other forms of NRT, bupropion, or varenicline), enrolled in a smoking cessation program or another cessation trial. Other exclusion criteria include use of an e-cigarette in the past 14 days, use of any other tobacco products (pipe, cigar, cigarillos, snuff, chewing tobacco, or hookah/shisha) in the past 30 days, an Alcohol Use Disorders Identification Test (AUDIT C) score of ≥ 7

Name of study: Assessing the use of electronic cigarettes (e-cigarettes) as a harm reduction strategy

for men and ≥ 5 for women, a Drug Abuse Screening Test-10 (DAST) score of ≥ 5 . Potential participants will also be excluded if they report having a history of asthma or other airways disease and heart disease.

Study Procedures

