After tracking their cigarette use, all participants will receive a 20-30 minute behavioral counseling consultation with a trained tobacco counselor. The counseling session will be scheduled at the baseline visit. Counselors will review each participant's smoking pattern from the three days of tracking and offer tailored behavioral and environmental change strategies including specific smoking reduction strategy options, such as eliminating cigarettes at work, in the home, or least favorite or most favorite cigarettes of the day, carrying only those cigarettes needed for that day, dropping cigarettes associated with less intense triggers first, avoiding smoking triggers, using oral or manual replacements, and other strategies to manage urges. Since there is inadequate evidence that any one of these strategies was more effective than another, participants will be encouraged to choose those that are most appealing. Goal setting, and barriers identification will be used to help participants improve confidence in their ability to reduce the number of cigarettes they smoked (Josephs 2008).

In Summary, the baseline visit includes 1) completion of baseline survey, 2) registering subject on text messaging program, 3) have subject practice using the text message program, 4) proactive using e-cigarette 5) make appointment for counseling session and for returning to pick up e-cigarettes.

Participants will be encouraged to reduce the number of cigarettes smoked daily to at least 50% of the total number of cigarettes smoked per day at baseline. This level was selected a priori as a clinically significant measure of reduction and to be a substantial enough reduction to address partial compensatory smoking (Glasgow 2009). Participants will be encouraged to substitute the use of the e-cigarettes for each cigarette they eliminate in order to reduce nicotine withdrawal symptoms.

After the counseling session, they will return to [name] to pick up their supply of disposable electronic cigarettes to last one week. They will be reimbursed for travel expenses. At the end of week

Name of study: Assessing the use of electronic cigarettes (e-cigarettes) as a harm reduction strategy

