1 of ecig use, they will be asked to return to replenish the e-cigarettes for another 2 weeks and to complete a second in-person assessment. The final study visit will be 3 weeks post starting e-cigarettes. We will conduct in depth interviews with a random sample of 10 participants in each intervention arm at the week 1 and 3 study visits. The first visit will focus on a process evaluation of the data collection experience and satisfaction with e-cigarette use while Week 3 interviews will focus on gaining more in-depth understanding of their experience (ease of use, satisfaction) with the product over time, e-cigarette related outcome expectancies and norms and explore intentions to quit and/or continuing dual use of cigarettes and e-cigarettes.

Figure 2. Assessments and intervention period**Data collection and Measures**

Baseline assessments: *Demographic information:* age, race/ethnicity, gender, years of education, employment, income; *Smoking history:* number of cigarettes smoked per day, number of years as regular smoker; use of other tobacco products or e-cigarettes, number of previous attempts in the past 12 months; *Other smoking related information:* self-rated importance and confidence to reduce and to quit, intention/readiness to quit using the readiness ladder, risk perceptions about e-cigarettes and combustible cigarettes, social norms related to using cigarettes and e-cigarettes, an assessment of urges to smoke using the QSU-Brief survey, other household members smoking at home; and the *Behavioral factors in smoking dependence scale* (Glover 2005). We will also measure carbon monoxide and collect saliva for cotinine measurement at baseline and study visit 3.

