Follow-up assessment study visits: At 1 and 3 weeks, we will assess withdrawal symptoms using the Minnesota Nicotine Withdrawal Scale (MNWS), e-cigarette use, cigarette use, quit attempts, and reduction in number of cigarettes used/day. Using Atkinson's treatment satisfaction scale, we will assess side effects associated with using the e-cigarette, convenience of use, perceived effectiveness, and global satisfaction with the product (Atkinson 2004). At the final study visit (week 3) we will also assess changes in baseline readiness to quit, intention to quit, norms related to smoking and using e-cigarettes, confidence in quitting and changes in intention to quit. At 12 weeks post starting e-cigarettes we will conduct follow up telephone surveys to assess current e-cigarette and cigarette use.

At each follow up assessment, RAs will complete a checklist for all of the activities including, completing surveys, and providing e-cigarettes. Note that we will schedule visits up to 4 times. If the subject misses all of those visits he/she will be considered lost to follow up. We will also attempt to contact subjects up to 10 times at different hours of the day and via text message to schedule or reschedule appointment to increase retention rates.

Table 1. In person survey assessments

Measures	Screener	Baseline	Wk 1	Wk 3	Wk 12 telephone
Socio demographics	X				
Smoking history and nicotine dependence		X			
Other tobacco products and marijuana use		X			
Readiness to quit		X		X	

Name of study: Assessing the use of electronic cigarettes (e-cigarettes) as a harm reduction strategy

Importance and confidence in quitting		X	X	
Smoking urges for traditional cigarettes (QSU-Brief)		X	X	
Self-efficacy questionnaire (SEQ12)		X	X	
Secondhand home policy and other smokers at home		X	X	
Risk perception (e-cigarettes)		X		
Social norms		X	X	
History of E-cigarette use		X	X	
Health status		X		
Behavioral dependence scale		X	X	
Current E-cigarettes use		X		
Treatment satisfaction scale (Side effects, Effectiveness, convenience related to e-cigarettes)			X	X
Minnesota Nicotine Withdrawal Scale			X	X
Current cigarette use		X	X	X
1. Someday, every day, not at all				
2. Number per day on days smoke (Self-report and CO and saliva validated abstinence)				
Quit attempt (24 hour) in past week			X	X
Acceptability and Receptivity to txt messages			X	X

Text message assessment:

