Table 2. Text messages and schedule

Rule (based on answer to the first question)	Text	3 days baseline tracking cig use				Intervention period			
		1 st	2 nd	3 rd	4 th	1 st	2 nd	3 rd	4 th
	Since your last report: Did you smoke a cigarette and/or E-cigarette? [no=0; cig=1; Ecig=2; both=3]	X	X	X	X	X	X	X	X
	Thinking about this morning, how many minutes after waking did you smoke your first cigarette? (Text 9999 if you did not smoke any cigarettes today)				X				X
	Thinking about this morning, how many minutes after waking did you use your first E-cig? (Text 9999 if you did not use any E-cigs today)								X
	Thinking about TODAY only: Do you want to smoke fewer cigarettes than usual? [0=Not at all ; 9=Very, Very Much]					X			
	Thinking about TODAY only: How hard would it be to use E-cigs ONLY? [0=Not at all ; 9=Extremely]					X			
If used cig	Since your last report: How many cigarettes did you smoked?	X	X	X	X	X	X	X	X
If used cig	How many minutes ago did you smoke a cigarette? [Text "0" if your are currently smoking]	X	X	X	X	X	X	X	X
If used cig only	On a scale of 0-9 how satisfying was your last cigarette? [0=Not at all – 9=Extremely Satisfying]	X	X	X	X	X	X	X	X
If used e-cig	Since your last report: How many separate times did you use an E-cigarette?					X	X	X	X
If used e-cig only	On average, how many puffs did you take with each use?					X	X	X	X
If used e-cig	How many minutes ago was your last E-cigarette puff? [Text "0" if you are currently using an E-cigarette]					X	X	X	X
If used e-cig	On a scale of 0-9 how satisfying was your last E-cigarette? [0=Not at all – 9=Extremely Satisfying]					X	X	X	X
	On a scale of 0-9, how much do you want to smoke a CIGARETTE right now? [0=Not at all – 9=Very, Very much]	X	X	X	X	X	X	X	X
	Thank you for completing the survey.	X	X	X	X	X	X	X	X

Primary outcome: For Aim 3, the primary outcome will be reduction in CPD and we will summarize this data as the proportion of participants who achieve 50% reduction in CPD at 3 weeks. Smoking reduction will be measured by a combination of self-report, text message data and changes in CO and saliva cotinine between baseline and end of treatment (3 weeks).

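### The primary outcome is a 50% cut in cigarettes per day, but its stated measures include changes in CO and cotinine, which do not count cigarettes, and no rule says how the measures combine

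*Combined protocol and SAP*

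**What the plan says.** The Primary outcome paragraph (after Table 2) summarizes the Aim 3 outcome as "the proportion of participants who achieve 50% reduction in CPD at 3 weeks". That is a count of cigarettes turned into a yes/no result. The next sentence gives the measurement: "Smoking reduction will be measured by a combination of self-report, text message data and changes in CO and saliva cotinine". The change runs from baseline to the end of treatment at 3 weeks. Data collection and Measures sets the biomarker schedule: "We will also measure carbon monoxide and collect saliva for cotinine measurement at baseline and study visit 3".

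The document gives no combination rule, no ranking of sources, no CO or cotinine change that counts as reduction, and no treatment of disagreement between a marker and the count.

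Three other places bear on the point:

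- Study Procedures says the 50% level was chosen in part "to be a substantial enough reduction to address partial compensatory smoking".
- Study design sets the arms as "e-cigarettes with nicotine cartridges or e-cigarettes with placebo cartridges (0mg"), and Study Procedures adds for both arms: "Participants will be encouraged to substitute the use of the e-cigarettes for each cigarette they eliminate".
- Table 1 links the markers to a different task: "Self-report and CO and saliva validated abstinence".

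The only numerical CO cut-off is for entry, in Study participants: "smokes at least 10 cigarettes a day (verified by a CO level of 8 ppm or above").

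**The concern.** A measure of CPD reduction should move with the number of cigarettes. CO moves with total smoke taken in, so it halves with CPD only if smoke per cigarette stays the same and none of the reading comes from other sources. The plan raises the possibility that smoke per cigarette does not stay the same. Cotinine moves with total nicotine, and the nicotine arm is encouraged to replace dropped cigarettes with another nicotine source while the placebo arm is not given one.

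The responder proportion is at stake. If the analysis team reads combination as a requirement that the sources agree, people who did halve their cigarettes can be classed as failures. For cotinine, this would fall on the nicotine arm more than on the placebo arm and would bias the comparison against nicotine e-cigarettes. Because the rule is open, it could also be settled after the data are seen.

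**Working it through.** The plan contains no calculation to reproduce: 50 per arm is stated without power, alpha or expected rates. What follows is illustrative.

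**Inputs from the document.** The endpoint is a 50% CPD reduction, so the remaining fraction is 0.5. Entry CO is at least 8 ppm. There are 50 participants per arm. Partial compensation is raised, but no size is given.

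**Assumptions, not in the document.** Rise in smoke per remaining cigarette, c: 0 to 50%. Background CO, b: 0 to 4 ppm. Log-scale SD of the week-3 to baseline CO ratio, s: 0.2 to 0.4. Two-sided alpha: 0.05.

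**Step 1. CO in an exact halver, no background.** CO fall = 1 − 0.5(1 + c). This gives 50% at c = 0, 40% at c = 20%, 30% at c = 40% and 25% at c = 50%. For CO itself to halve, CPD must fall by 1 − 0.5/(1 + c): 58% at c = 20% and 67% at c = 50%.

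**Step 2. With background.** Week-3 CO = (CO0 − b) × 0.5 × (1 + c) + b.

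- With b = 2 and c = 25%, entry CO of 8 ppm becomes 6 × 0.625 + 2 = 5.75, a fall of 28%. At 12 and 20 ppm the falls are 31% and 34%.
- Over the whole assumed range, the fall is 12.5–50% at 8 ppm, 17–50% at 12 ppm and 20–50% at 20 ppm. The upper end, 50%, is no distortion at all.
- The CPD cut needed for CO to halve is 1 − (0.5 CO0 − b)/((CO0 − b)(1 + c)). At b = 2 and c = 25% it is 73%, 68% and 64%. Over the whole range it runs from 50% (b = 0, c = 0) to 100% (8 ppm, b = 4).

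**Step 3. Chance that an exact halver passes a CO rule, no background.** For a required CO fall t, the probability is Φ((ln(1 − t) − ln(0.5(1 + c)))/s). Example with t = 0.5, c = 0.2, s = 0.4: (ln 0.5 − ln 0.6)/0.4 = −0.456, so 32.4%. Ranges are for s from 0.2 to 0.4.

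| Required CO fall | c = 0 | c = 20% | c = 40% |
|---|---|---|---|
| at least 50% | 50% | 18.1–32.4% | 4.6–20.0% |
| at least 25% | 84.5–97.9% | 71.2–86.8% | 56.8–63.5% |
| any fall | 95.8–100% | 89.9–99.5% | 81.4–96.3% |

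The loss is large when CO must fall about as much as CPD, and smaller under milder rules. If CO is only supportive there is no loss.

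**Step 4. Cotinine.** Let e be nicotine from the e-cigarette as a fraction of baseline nicotine intake. In an exact halver the cotinine ratio is 0.5(1 + c) + e, and e = 0 on placebo. At c = 0 the placebo halver falls 50% and the nicotine-arm halver falls 50% − e. If the device replaced all the nicotine in the dropped half (e = 0.5), the nicotine-arm halver would show no fall. The document gives no value for e, but whatever it is, it is present in one arm only.

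**Step 5. Effect on the comparison, at assumed true responder rates of 50% and 30%.** Power with 50 per arm is 53%. If a CO rule loses 30% of true halvers in both arms, the rates become 35% and 21% and power is 34%. If it loses 50%, they become 25% and 15% and power is 24%. If a cotinine rule lost 40% of halvers in the nicotine arm alone, 0.50 × 0.6 = 0.30 and the observed difference would vanish.

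**The case against.** The strongest reply is that the plan contains no pass/fail test on either marker. The endpoint sentence is stated on CPD alone, and Table 1 attaches CO and saliva to abstinence, which suits a corroborating role. If that is the intent, no halver is lost. This stands, and it limits the finding to what an unstated rule could do.

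A reader might go further and infer that true halvers will be scored as failures. The documents do not support that, because they set no CO threshold and do not require the sources to agree. A reader might also infer that the CO error favours one arm because placebo users would smoke their remaining cigarettes harder. Nothing in the documents says so; it would need compensation to differ by arm. The arm-dependent marker is cotinine. Nor does the plan overlook compensation: it offers the 50% level as its answer. But a larger CPD target does not make CO a measure of CPD.

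Two further replies have some weight. Biomarkers are the only check on self-report in participants urged to halve their smoking, so removing them from the definition has a cost. And arm differences are called exploratory under Secondary outcomes, which lowers the stakes, although Aim 3 is itself a comparison of arms.

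**Conclusion.** The point holds in a conditional form. The primary outcome is a cigarette count, two of its four named measures do not count cigarettes, and the way they combine is undefined. That much comes from the text, together with what the markers measure. Any rule requiring a sizeable fall in CO or cotinine could misclassify true halvers, and with cotinine the misclassification would differ by arm.

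The size is not fixed by the documents. It runs from no loss, if the markers are only supportive, to most exact halvers lost, if CO must also fall by 50% and compensation is 20% or more. Every figure for compensation, background CO, reading variability and responder rate is an assumption.

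Writing down a combination rule would remove the ambiguity, but it would not cure the mismatch if the rule still required a marker to fall. The entry wording, which presents CO of 8 ppm as verifying 10 cigarettes a day, has the same looseness. It is a minor clarification only, and correcting it changes no eligibility decision.

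**What to change.** In the Primary outcome paragraph, define the week-3 responder as a participant whose CPD has fallen by 50% or more, on CPD counts alone and from one named source. Two sources are available:

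- **Text messages:** the three tracking days as baseline and a stated week-3 window (for example, days 15 to 21 of the 21 intervention days), with a rule for unanswered prompts.
- **Visit self-report:** the baseline survey and the week-3 visit.

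Use the source not chosen as a sensitivity analysis, and say how disagreement between the two is handled. Remove CO and cotinine from the responder definition.

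Add two entries under Secondary outcomes. The first is smoke exposure: week-3 CO by arm, adjusted for baseline CO, in all participants and among CPD responders. The second is total nicotine exposure: week-3 cotinine by arm, described as including e-cigarette nicotine. The general summary of visit measures in Data Analysis and Data Monitoring does not specify either analysis.

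Optionally, reword the entry criterion to say that CO of 8 ppm or above confirms recent smoking and that the 10-a-day count is self-reported.

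The cost is wording and a few extra summaries, with no new data. The downside is that the primary outcome then rests on self-report, with biomarkers shown beside it. The gain is a responder that matches the stated endpoint, plus a direct answer to whether smoke exposure fell, which CPD cannot give.

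### Saliva cotinine is listed as a measure of smoking reduction, but at week 3 it cannot measure smoking alike in the two arms, because only one arm's product contains nicotine

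*Combined protocol and SAP*

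**What the plan says.** The Primary outcome paragraph (after Table 2) has two sentences that matter here. The first names reduction in CPD as the outcome for Aim 3, summarised as "the proportion of participants who achieve 50% reduction in CPD at 3 weeks". The second describes smoking reduction as "measured by a combination of self-report, text message data and changes in CO and saliva cotinine between baseline and end of treatment". Table 1, under current cigarette use, has the entry "Number per day on days smoke (Self-report and CO and saliva validated abstinence".

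On timing, the Baseline assessments paragraph says: "We will also measure carbon monoxide and collect saliva for cotinine measurement at baseline and study visit 3". Under Study Procedures, "The final study visit will be 3 weeks post starting e-cigarettes", so the second sample comes at the end of the product-use period, which the Text message assessment section puts at 21 days.

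On exposure, the Study design section gives the arms as "e-cigarettes with nicotine cartridges or e-cigarettes with placebo cartridges (0mg"). Study Procedures adds: "Participants will be encouraged to substitute the use of the e-cigarettes for each cigarette they eliminate in order to reduce nicotine withdrawal symptoms".

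The documents give no rule for combining the four sources, no cotinine cut-off and no adjustment for nicotine from the e-cigarette. The Data Analysis and Data Monitoring section does not mention cotinine.

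**The concern.** One premise comes from outside the documents and is an assumption here: cotinine reflects nicotine intake whatever its source. At baseline this does little harm. The exclusion criteria remove current nicotine replacement, e-cigarette use in the past 14 days and other tobacco in the past 30 days, so cotinine then tracks mainly cigarettes in both arms. At week 3 it still does so on placebo, apart from any other tobacco taken up during the study. On nicotine it also counts the study product, which participants are encouraged to use in place of each cigarette they drop. Randomisation cannot balance this, because the distortion comes from the assigned treatment.

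Two things follow. Change in cotinine, read as smoking reduction and compared between arms, understates reduction on nicotine. And a nicotine-arm participant who has stopped smoking but still uses the product could fail saliva validation where a placebo participant with the same smoking passes. Aim 3 and the third research question are the between-arm comparison that this would distort.

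**Working it through.** The plan states no test, error rate, effect size or cotinine rule, so it has no figure to reproduce. What follows is an illustration.

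**Inputs.** From the protocol: 50 per arm, a 50% responder threshold and four listed sources. Assumed: a two-sided 5% pooled two-proportion test; true CPD reduction R, normal with the same distribution in both arms, mean 35%, 50% or 60% and SD 25% or 35% (six settings); cotinine proportional to nicotine intake; self-report, text data and CO all falling with CPD alike in both arms; and a share f of each dropped cigarette's nicotine replaced by the nicotine product.

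**Step 1: one participant.** Cotinine falls by R on placebo and by R(1 - f) on nicotine. For a true 50% CPD cut, that is 50% on placebo against 50% × (1 - 0.25) = 37.5% at f = 25%, or 50% × (1 - 0.5) = 25% at f = 50%.

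**Step 2: CPD alone decides.** The threshold is R ≥ 0.50 in both arms. Responder rates are equal, and exact binomial enumeration gives false rejection of 4.9-5.7% over the six settings. There is no bias.

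**Step 3: four sources equally weighted.** The average fall on nicotine is [3R + R(1 - f)]/4 = R(1 - f/4), so a nicotine-arm participant needs R ≥ 0.5/(1 - f/4), against 0.5 on placebo.

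| f | CPD cut needed on nicotine | Nicotine-arm responders lower by | False rejection |
|---|---|---|---|
| 10% | 0.5/0.975 = 51.3% | 1-2 points | 5-6% |
| 25% | 0.5/0.9375 = 53.3% | 3-5 points | 6-9% |
| 50% | 0.5/0.875 = 57.1% | 7-11 points | 12-22% |

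One setting in full, with mean 50%, SD 25% and f = 25%: placebo responders are 1 - Φ(0) = 50.0%, and nicotine responders are 1 - Φ((0.533 - 0.50)/0.25) = 44.7%. The gap is 5.3 points and false rejection is 9.2%.

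**Step 4: more weight on cotinine.** If only CPD and cotinine are averaged, the cut needed is 0.5/(1 - f/2). False rejection is then 6-8%, 12-22% or 41-77% at f = 10%, 25% or 50%.

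**Step 5: compensatory smoking.** The protocol expects some, since it chose the 50% target "to be a substantial enough reduction to address partial compensatory smoking". Suppose placebo users alone recover 20% of each dropped cigarette's nicotine by smoking the rest harder, counted in cotinine only (a simplification). Under the four-source rule, the placebo cut becomes 0.5/(1 - 0.2/4) = 52.6%. At f = 25% (53.3% on nicotine) the bias nearly cancels; at f = 10% (51.3%) it reverses and favours nicotine.

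**The case against.** The strongest reply is that the outcome is a CPD proportion. The first sentence of the paragraph says so, the analysis section plans only descriptive summaries for visit measures and never mentions cotinine, and on that reading the responder rate is unbiased. This stands as far as the responder rate goes. It does not rescue the second sentence, which calls cotinine change a measure of smoking reduction, or Table 1, which uses saliva to validate abstinence.

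A reader might infer from Step 4, or from a rule requiring CPD and cotinine each to fall by 50%, that the trial faces false rejection of 41-77%. The documents do not support that. Neither rule appears in them: four sources are listed, and the 50% cut is applied to CPD only. With equal weights, the inflation is modest unless much of the nicotine is replaced, and f itself has no anchor in the documents.

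The abstinence limb is also limited. Table 1 is a measurement schedule, it gives no cut-off, and abstinence is not a listed primary or secondary outcome. Finally, the argument concerns cotinine alone. Nothing in the documents shows that CO behaves differently by arm at equal smoking, so there is no case here for removing CO from the measure as well.

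**Conclusion.** The plan is wrong as written on this point, at lower priority. Given the pharmacological premise, cotinine change from baseline to week 3 is not the same measure of smoking in the two arms, and should not be read or compared as smoking reduction. That conclusion needs no combining rule.

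A reader might go further and conclude that the primary responder comparison is biased. That is conditional: there is no bias if CPD alone decides. If all four sources count equally, the nicotine arm loses 1-2, 3-5 or 7-11 points at f = 10%, 25% or 50%. The direction is usually against nicotine, but not certainly, since compensation on placebo can cancel or reverse it.

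The stakes are limited. This is a pilot, and the Secondary outcomes paragraph calls differences between arms exploratory, although Aim 3 and the third research question pose that comparison. The sizes rest on the assumed reduction distribution, replacement share, weights and test.

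**What to change.** In the Primary outcome paragraph, delete saliva cotinine from the smoking-reduction measure. Keep the 50% responder definition on CPD, with expired CO as the biochemical measure in both arms. Add a sentence such as: *Saliva cotinine will be reported by arm as total nicotine exposure and will not be used to measure or compare smoking reduction.* In Table 1, drop saliva from the abstinence entry so that abstinence is validated by CO only.

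The cost is wording: every sample is still collected and reported. The downside is reliance on CO, which (again from general knowledge) covers a shorter window than cotinine and can be raised by smoking marijuana. The protocol already records marijuana use, so CO results should be read alongside it. How CPD and CO are to be combined, which CPD source and window to use, and what CO cut-off marks abstinence are separate gaps that this change does not settle.

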Secondary outcomes: We will assess potential side effects associated with e-cigarette use, additional use of other tobacco products and/or marijuana, satisfaction with the e-cigarettes, nicotine urges/cravings and withdrawal symptoms. An exploratory secondary aim includes assessing differences in the primary and secondary outcomes between the intervention arms.

Name of study: Assessing the use of electronic cigarettes (e-cigarettes) as a harm reduction strategy

Feasibility measures include: 1) Percentage of subjects screened who are eligible and enroll, 2) percentage retained at 3 and 12 weeks, 3) retention across study conditions, 4) consistency in tracking use of e-cigarettes and cigarettes, and 5) satisfaction with e-cigarettes.

Characteristics of the Research Population

Described above under the study participants section.

Number of Subjects

We expect to enroll 100 smokers total, 50 in each arm.

Gender of Subjects

We would ensure equitable inclusion of both men and women in this study.

Age of Subjects

All subjects will be 21-35. We are particularly interested in studying the effectiveness of e-cigarettes as a harm reduction strategy among young adults as this is an understudied population and one that has demonstrated exceptionally high rates of adoption of this product.

Racial and Ethnic Origin

We will recruit across all racial and ethnic groups.

Inclusion Criteria

All subjects must be between 21-35 years old, daily smokers, smoke at least 10 cigarettes per day, interested in reducing CPDs, able to provide consent, use a cell phone, are willing/able to receive and respond to daily text messages regarding their cigarette use and e-cigarette use on their cell phone, and are willing to use an e-cigarette for 3 weeks.

Exclusion Criteria

Subjects will be excluded if they are pregnant and/or breast feeding (self-reported), are currently using smoking cessation medications (including other forms of NRT, bupropion, or varenicline), are enrolled in a smoking cessation program or another cessation trial, have used an e-cigarette in the past 14 days, have used any other tobacco products (pipe, cigar, cigarillos, snuff, chewing tobacco, rolling tobacco, or hookah/shisha) in the past 30 days, score ≥ 7 (men) or ≥ 5 (women) on the Alcohol Use Disorders Identification Test (AUDIT-C), score ≥ 5 on the Drug Abuse Screening Test-10 (DAST), or report having a history of asthma, other airways diseases, or heart disease.

Data Analysis and Data Monitoring

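### Use of other tobacco or marijuana is a secondary outcome, but the written schedule asks about it only at baseline, so there would be no follow-up data to report

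*Combined protocol and SAP*

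**What the plan says.** The Secondary outcomes paragraph lists the outcome: "We will assess potential side effects associated with e-cigarette use, additional use of other tobacco products and/or marijuana, satisfaction with the e-cigarettes". It then adds: "An exploratory secondary aim includes assessing differences in the primary and secondary outcomes between the intervention arms". Use of other products is thus both an outcome to be reported and one to be compared between the nicotine and placebo arms.

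Data collection is described in several places:

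- **Table 1.** The row "Other tobacco products and marijuana use" carries one mark, under Baseline.
- **Baseline assessments.** The smoking-history items include "use of other tobacco products or e-cigarettes, number of previous attempts in the past 12 months".
- **Follow-up visits.** "At 1 and 3 weeks, we will assess withdrawal symptoms using the Minnesota Nicotine Withdrawal Scale (MNWS), e-cigarette use, cigarette use, quit attempts", together with reduction in cigarettes per day, satisfaction and side effects. For the last visit: "At the final study visit (week 3) we will also assess changes in baseline readiness to quit, intention to quit, norms related to smoking".
- **Week 12 call.** "At 12 weeks post starting e-cigarettes we will conduct follow up telephone surveys to assess current e-cigarette and cigarette use".
- **In-depth interviews.** At week 3 these are to cover product experience, expectancies and norms, and to "explore intentions to quit and/or continuing dual use of cigarettes and e-cigarettes".

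The Data Analysis section summarizes each measure at the time points at which it was collected. It adds no further source of data.

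**The concern.** Additional use can only be seen after participants start on e-cigarettes, and a comparison of arms needs measurements after randomized product has been issued. The schedule gives the item no such time point. Followed as written, the plan would produce a baseline table for this outcome and nothing else.

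The loss is descriptive, but it bears on the trial's purpose. Participants are encouraged to cut their cigarettes by at least half as harm reduction. Whether some of them turn to cigars, hookah or marijuana while doing so is a natural question, and the sponsor chose it as an outcome. If it is not asked during the trial, contemporaneous answers cannot be recovered later.

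**Working it through.** The plan gives no figure to reproduce for this outcome. The check sets the outcome against every described source of data.

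**1. Is the Table 1 mark read correctly?** Rows after the page break in Table 1 have lost a column in the extracted text. This row lies before the break with its columns intact. The row beneath it, on readiness to quit, shows separate marks at Baseline and week 3. The Baseline-only reading is therefore not an extraction artefact.

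**2. Does any other source ask about it after baseline?**

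| Source | What it covers | Other tobacco or marijuana named? |
|---|---|---|
| Weeks 1 and 3, narrative | Withdrawal, e-cigarettes, cigarettes, quit attempts, satisfaction, side effects | No |
| Week 3, added items | Readiness, intention, norms, confidence | No |
| Week 12 call | E-cigarettes and cigarettes | No |
| Text messages (Table 2) | Opening question coded none, cigarette, e-cigarette or both; related follow-up items | No |
| Interviews, 10 per arm | Product experience, expectancies, norms, quit intentions, dual use | No |
| Forms at each contact (Protection Against Risks) | Side effects and adverse events | No |

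The count is 0 of 3 post-baseline assessments. The texts run to 24 × 4 = 96 prompts, of which 21 × 4 = 84 fall in the intervention period, and no question in them covers another product. CO and cotinine do not identify which other product was used, so they do not fill the gap.

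**3. Could baseline serve instead?** No. E-cigarettes are collected after the baseline visit, the three days of tracking and the counseling session. Other tobacco use in the past 30 days is an exclusion, so the baseline answer should be near zero by design. Marijuana is not a listed exclusion, although the DAST-10 cut-off may remove some heavier drug users. Baseline may therefore record marijuana use at entry, but not additional use.

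**4. What would one added item at week 3 give?** This describes the remedy, not the defect. The documents state no expected retention; 70% to 100% is assumed, giving 50 × 0.70 = 35 to 50 × 1.00 = 50 answers per arm. The use rates are also assumed. Exact (Clopper-Pearson) 95% intervals:

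| Assumed use | 35 per arm | 50 per arm |
|---|---|---|
| None | 0/35: 0 to 10.0% | 0/50: 0 to 7.1% |
| About 10% | 4/35: 3.2 to 26.7% | 5/50: 3.3 to 21.8% |
| 20% | 7/35: 8.4 to 36.9% | 10/50: 10.0 to 33.7% |

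With no users, the upper limit is 1 − 0.025^(1/n). For both arms together this is 5.1% (0/70) or 3.6% (0/100).

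For the arm comparison, take 10/50 against 5/50. The difference is 10 percentage points, with standard error √(0.2 × 0.8/50 + 0.1 × 0.9/50) = √0.0050 = 0.0707. The approximate 95% interval is 10 ± 1.96 × 7.07, or −3.9 to 23.9 points. Even with full retention, a doubling of use would not be clearly distinguished from no difference.

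**The case against.** The strongest reply is that silence in these lists proves little. The narrative lists are not exhaustive: Table 1 gives the smoking-urge, self-efficacy, home-policy and behavioral-dependence items a second mark, evidently after baseline, yet the follow-up narrative names none of them. The baseline narrative omits marijuana although Table 1 schedules it there. Table 1 has faults of its own: it marks demographics at the screener only, while the text places them at baseline, and its row on current e-cigarette use shows one mark although the text assesses this at weeks 1, 3 and 12. Since the outcome paragraph says the use will be assessed, the omission may lie in the table and not in the data collection.

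This stands as a limit on the claim. The follow-up questionnaires are not in the documents, and Figure 2, which shows the assessments, could not be seen. What is established is a disagreement between the stated outcome and the written schedule, not that the question will certainly go unasked. On this item, however, the table and the narrative agree, and the documents need correcting under either explanation.

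It is also fair to say that this is one secondary outcome in a pilot, with an exploratory comparison, and that no feasibility measure depends on it. That limits its importance, but a named outcome with no scheduled measurement should still be put right.

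**Conclusion.** The concern holds. The plan names use of other tobacco or marijuana as a secondary outcome with an exploratory arm comparison, and schedules it at 0 of 3 post-baseline assessments. Followed as written, it yields no estimate of additional use in either arm and no arm difference. Confidence is high for this mismatch and does not extend to the content of the unseen questionnaires. The primary outcome, reduction in cigarettes per day, is unaffected. The point should be corrected, but it does not threaten the trial's main result.

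**What to change.** **Preferred.** In Table 1 and the follow-up narrative, repeat the existing item at least at week 3, and preferably also at weeks 1 and 12. Ask about use since e-cigarettes were issued. Report number and percentage by arm with exact 95% intervals, other tobacco and marijuana separately, with marijuana set against its baseline answer. Label the arm comparison exploratory.

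**Otherwise.** Remove the item from the secondary outcomes, or relabel it a baseline descriptor. If the follow-up questionnaires already contain it, correct Table 1 and the narrative lists to show this.

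**Cost.** Repeating the item takes a few minutes per participant at a contact already planned, plus a small form change. The answers would be unverified self-report, and the arm comparison would remain imprecise. Removing the outcome costs nothing in data collection but gives up any information on take-up of other products.
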